4.5 Informed Consent

Once it is determined that a participant may qualify for the protocol and is interested in participating, written informed consent or legal guardian permission and participant assent will be obtained. Study details including the information to be collected and the evaluations and assessments involved will be discussed with potential participants who show interest in the study and all questions will be answered.

The initial informed consent procedure is intended to be conducted at the clinical site prior to the Entry (Year 0) visit. If circumstances preclude an in-person Entry (Year 0) visit, informed consent may be conducted remotely along with the remote Entry visit. Remote consenting (initial and re-consent) will be conducted using the web-based ICF or via telephone. PHACS Leadership will work with the clinical sites to ensure that the web-based ICF used at each participating site has been approved by the HLC IRB as well as their local IRB, when indicated. If remote consenting should occur, clinical site staff will be available for phone consultation to address questions or concerns.

Clinical site staff will monitor whether the mental capacity of a participant changes throughout the course of the study (see Section 8.2). Each site employs psychology staff that can advise when a participant's competence to give continuing consent is in question, and they will contact the HLC IRB or local IRB for guidance, as needed.

When a participant is unable or unwilling to continue to be followed in-person at the clinical site after the Entry visit, they will be encouraged to transfer to another AMP Up site or to continue to be followed remotely by the originating site, if transfer to a new site is not possible. If neither of these options are possible, the participant may be consented to continue study participation through the PHACS Data Resources Core (DRC) at the Harvard T. H. Chan School of Public Health (HSPH). The informed consent process at HSPH will occur remotely either by using the web-based ICF or via telephone. HSPH staff will be available for telephone consultation when web-based informed consent is conducted.

The web-based ICF will include verification of comprehension and require participants to acknowledge that they have read and agree to the ICF by checking a box following each section of the consent. Verification of identification during the consent process will be confirmed through the use of a consent identification number (CIN) provided to the participant by the clinical site prior to study enrollment. Security questions may be employed for further verification.

4.6 Enrollment Procedures

When a participant is eligible for the study and informed consent has been obtained, the site will use the Study Enrollment System (SES) at Frontier Science, the Data Management Center (DMC) for PHACS, to enter participant and eligibility information. Participants who were previously enrolled in PHACS will continue to use their PHACS participant identification number (PID). Participants recruited from International Maternal Pediatric Adolescent AIDS Clinical Trials Network (IMPAACT) or AIDS Clinical Trials Group (ACTG) will retain their IMPAACT or ACTG PID. The SES will generate a study identification number/personal identification number (SID/PIN) specific to the AMP Up study for participants who are confirmed eligible and enrolled. In AMP Up, the SID will serve as the participant's PIN that will be used as the participant identifier in web-based assessments.

At initial consent or re-consent (for participants previously enrolled in protocol version 1.0), participants will be asked to consent to provide their address information for the purpose of future geocoding. The address information will be stored at the clinical site and will not be part of the AMP Up database.

4.7 Co-Enrollment Guidelines

Enrollment of AMP Up participants in other studies (with or without similar goals/data collection as AMP Up) is at the discretion of clinical site principal investigators. However, they must take into account any issues that enrollment in the additional study may require, and which may compromise the site's ability to fulfill the requirements of PHACS.

Children born to female YAPHIV AMP Up participants are encouraged to be enrolled along with their mothers in the SMARTT dynamic cohort.

Participants who indicate they would like to be contacted for studies opening in the future will provide their contact information to the clinical site. Each site will maintain this information and, in the event a participant changes their mind and no longer wishes to be contacted, the clinical site will track these requests and update their documentation accordingly.

5.0 CLINICAL AND LABORATORY EVALUATIONS

The following clinical and laboratory evaluations will be performed on each participant, after signed informed consent is obtained, as part of participation in this study. See Appendices I and II for a tabulated summary of the evaluations described below and their schedule of completion.

The study visits at Entry (Year 0) and every 3 years starting at Year 3 (e.g., Years 3, 6, 9, 12...) are intended to be conducted in-person. If circumstances preclude an in-person visit, the visit can be conducted remotely, e.g., clinical assessment data will be collected through chart abstraction (when available), surveys and questionnaires may be completed via telephone (with Protocol Team approval), and specimens may be self-collected and shipped to the clinical site. Any remaining assessments that cannot be completed (e.g., NIH Toolbox, body measurements, Block Physical Activity Screener, blood draw for repository specimens) will be considered missed. However, missed assessments may be completed at the next annual visit, with Protocol Team approval (see Section 8.1).

5.1 Entry Visit (Year 0) Evaluations

For participants previously enrolled in other studies such as WITS, IMPAACT 219/219c, 1025, and 1074, and the CDC LEGACY study and other PHACS studies who agreed to share their data from these other studies with AMP Up, the Protocol Team will abstract relevant information on medications, viral load and CD4 cell count, and major medical events from the study database of these other studies; clinical site staff will abstract any remaining data from the medical record.

Entry (Year 0) visit evaluations for all participants will include chart abstraction, clinical assessments, real-time laboratory testing, collection of specimens for central testing and the PHACS Repository, hearing, language (for a subset of participant only; see Section 9.4), cognitive and mental health assessments, the Block Physical Activity Screener, and a web-based survey (see Section 9.1 and Appendices I and II). The web-based survey can be conducted either at the clinic during the in-person visit or remotely. The entire Entry visit is expected to take up to 4 hours to complete.

5.2 In-Person Evaluations

As with the Entry (Year 0) visit evaluations, evaluations every 3 years starting at Year 3 (e.g., Years 3, 6, 9, 12...) will include chart abstraction, clinical assessments, real-time laboratory testing, collection of specimens for central testing and the PHACS Repository, cognitive, hearing, and mental health assessments, the Block Physical Activity Screener, and the web-based survey. The web-based survey can be conducted either in-person or remotely. Each of the in-person follow-up visits is expected to take up to 3 hours to complete.

5.3 Web-Based Surveys, Specimen Collection, and Chart Abstraction

During years without in-person visits (e.g., Years 1, 2, 4, 5, 7, 8, 10, 11, 13, 14...) study assessments will consist of web-based surveys, self-collection of specimens for STI testing (real-time and research Aptima testing), and chart abstraction. Web-based surveys and specimen collection can be completed outside of the clinical site. However, participants will have the option to complete them at the clinical site if they prefer. Chart abstraction will be completed annually in the clinic by clinical site staff.

5.4 Additional Web-based Surveys

From time to time, technological developments, events impacting public health, or geopolitical events may be expected to impact the health and wellbeing of YAPHIV and YAPHEU. If such events occur, additional surveys may be developed to address these issues. These surveys would first be submitted to the HLC IRB as a protocol modification. Once approved by the HLC IRB, these surveys would be administered to participants. These additional surveys may be administered by clinical site staff as interviews or as web-based surveys (completed in clinic or sent by the site to participants as survey links) or sent as survey links by the PHACS DMC at Frontier Science (if the participant gave their permission for the DMC to receive and retain their contact information from the site).

6.0 DATA AND SPECIMEN COLLECTION AND SITE MONITORING

6.1 Data Records

For medical record reviews and other non-web-based data collection, case report forms (CRF)/data entry screens will be provided for each participant. Participants must not be identified by name on any CRFs, web-based assessments, laboratory specimens, clinical evaluation results, and laboratory results that are part of the research records. Participants are to be identified by the PID and SID/PIN numbers assigned by PHACS. Study research records with PID and SID/PIN must be stored separately from source documents that include personal identifiers.

Web-based data collection will utilize multiple sources. The majority of the annual web-based data collection (“web-based surveys”) as well as collection of participant contact information (see Section 8.3) will be conducted via the commercial software tool Illume that was designed by DatStat, Inc. specifically for creating web-based data collection instruments. The Illume software tool uses secure hypertext transfer protocol secure (HTTPS) connections that adhere to the Food and Drug Administration (FDA) guidelines for secure electronic data capture. (See Appendix IV for a detailed description of DatStat measures for data security and user confidentiality for web-based surveys). The collected data will be stored on DatStat's server and transferred to the PHACS central database at Frontier Science. Respondent data are protected by state-of-the-art security controls including firewalls and encryption. Access to the

server will be highly restrictive and limited to a small number of project staff who have been authorized by PHACS Leadership to have access.

The web-based Block Physical Activity Screener will be used to collect physical activity data at the in-person visits (Entry and every 3 years). Hosted by NutritionQuest, their Data-on-Demand web-based survey system uses the standard Secure Sockets Layer (SSL) encryption protocol to ensure that data are transmitted securely. The database itself is password protected, and passwords are changed regularly. Data are retained until indicated by project investigators. The servers hosting all NutritionQuest web-based services are dedicated (not shared) and are located in rooms with 24-hour security. Every effort is made to keep identifying information secure and confidential.

Neurocognitive data will be collected at the in-person visits (Entry and every 3 years) using the NIH Toolbox instruments available through the NIH Toolbox iPad App. All data submitted are encrypted and stored on a secure server. Security measures designed to protect against the loss, misuse, or alteration of data are also in place at the physical facilities where servers are housed at Northwestern University in Chicago, IL, and the National Institutes of Health (NIH).

The PHACS DMC will use HTTPS to securely download all data collected via the web from all of the sources outlined above to the PHACS central database. In addition, the policies and procedures governing the collection, storage and transfer of all data collected via the web will be reviewed annually by the PHACS Leadership, or immediately in the event that any breaches are discovered or reported.

6.2 Data Collection

For CRFs/data entry screens used at the clinical site, instructions on recording study data on the CRFs and the entry of data into the computerized database will be provided by the PHACS DMC. The DMC will provide training, as needed, for clinical site staff on the use of the web-based survey and on how to access the Block Physical Activity instrument. NIH Toolbox training will be conducted through a self-directed web-based training and supplemented by a central web-based or individual training session depending on site training needs.

At the Entry visit, clinical site staff will access the web-based survey via links provided to them by the DMC. The Block Physical Activity Screener and the NIH Toolbox will be accessed through the website and the iPad application, respectively, hosted by the institutions maintaining the respective surveys. Clinical site staff will introduce participants to each survey and explain the process of completing them. Participants will then complete the surveys. The web-based survey may be completed remotely if the participant cannot go to the clinic to complete it.

Most of the questions in the AMP Up web-based survey are incorporated into a single primary survey, while other questions may be administered separately as short, stand-alone surveys. Only one stand-alone survey will be administered each year. Participants will receive a link to the longer, primary survey and - if applicable - a separate link to the stand-alone survey. The participant can choose to complete both the primary and the stand-alone survey at the same time, or they can complete the stand-alone survey at a later time. If the stand-alone survey is completed at a later time, participants will receive the link either from the clinical site or from the PHACS DMC at Frontier Science (the latter only if participants gave their permission for the DMC to receive their information).

When participants complete the follow-up web-based survey outside the clinic, they can link to the web-based survey either through the links provided to them by the clinical site staff or Frontier Science or

through the AMP Up participant website (see Section 8.5). Participants will log in to the website using a unique, participant-specific username and passcode to access the link to the survey they need to complete.

6.3 Data Quality Assurance

Clinical site monitoring for protocol and regulatory compliance will be conducted by Westat at each participating PHACS site.

The clinical site principal investigator will make study documents (e.g., ICFs, CRFs, electronic medical records) and pertinent hospital or clinic records readily available for inspection by the local IRB, HLC IRB, the NIH, the Office of Human Research Protection (OHRP), and the site monitors acting on behalf of the NIH to confirm the study data and regulatory compliance.

Note: Participating sites are responsible for specifying these individuals and the PHACS investigators as recipients of private health information in the individual's authorization required under the Health Insurance Portability and Accountability Act of 1996 (HIPAA) Privacy Rule.

6.4 Testing of Specimens in Real-Time

YAPHEU will have an HIV test performed in real-time at a local clinical lab at the Years 3 and 9 in-person study visits.

For participants with neither *N. gonorrhoeae* nor *C. trachomatis* testing results available in the medical records during the 12 months prior to the visit, urine for males and vaginal swab (preferred, or urine if swab is declined) for females will be self-collected as per local clinical lab requirements for real-time STI testing at the local clinical lab. At the Entry and every 3 years starting at Year 3 (e.g., Years 3, 6, 9, 12,...), the sample will be self-collected at the clinic and at other time points self-collected either at the clinic, a commercial lab, or at home.

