2.2 Domain-Specific Aims and Hypotheses

2.2.1 Infectious and Non-Infectious Complications of HIV and Its Treatment

Specific Aims:

- To evaluate the long-term immunologic and virologic course of YAPHIV, including immune competence and activation, disease progression, viral resistance, and the response to changes in therapy.
- To identify cofactors which impact the short- and long-term course of HIV disease, including incident co-infections and host genetics.
- To evaluate the incidence and course of HIV end-organ disease (i.e., renal, hepatic, cardiac, pulmonary, and peripheral and central nervous system) and HIV-associated malignancies and mortality of YAPHIV, and to describe the relationship of these outcomes with HIV virologic status, ART, immune impairment, and chronic immune activation.
- To contribute to HIV remission/cure studies by understanding the viral dynamics and compartmentalization of PHIV in the context of novel HIV therapeutics, age at ART initiation, long-term viral suppression, immunologic control, and the presence and size of the viral reservoir.
- To evaluate access to testing for SARS-CoV-2, access to and acceptance of prevention strategies for SARS-CoV-2, and acceptance of testing, treatment, and prevention strategies for other important infections among YAPHIV and YAPHEU.
- To assess vaccine acceptance among YAPHIV and YAHEU including receipt and intent to receive a SARS-CoV-2 vaccine and explore reasons for acceptance or hesitancy.
- To define the oral health of YAPHIV and YAPHEU and to identify risk factors associated with declining oral health.
- Among YAPHIV, to determine risk behaviors for HIV transmission and their understanding of “U = U” as an approach to the prevention of HIV transmission.
- Among YAPHEU, to determine their level of knowledge about and use of PrEP and their rates of HIV acquisition.

Hypotheses:

- Participants without viral suppression will experience disease progression, increasing viral resistance, and increasing immune impairment. These changes will be increasingly difficult to reverse with advances in ART.
- Immune suppression early in life (or later in life with loss of virologic control) results in an impaired immune response to immunizations and infections, resulting in long-term susceptibility to infection. Immunization once immune reconstitution is achieved will be necessary for most vaccines.

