- Congenital and acquired CMV infection results in HIV disease progression and potentiates end-organ disease.
- Specific host genetic polymorphisms and epigenetic changes are associated with HIV disease progression, response to ART, response to co-infections, and specific end-organ disease.
- Chronic immune activation, lack of viral suppression, decreased CD4 counts, and ARV exposures will be independently associated with HIV disease progression and end-organ diseases.
- YAPHIV who are virally suppressed will have a higher incidence of end-organ disease than YAPHEU, related to immune activation.
- The viral dynamics, reservoir size, and compartmentalization of PHIV and the host response to the infection will be different than that of young adults without PHIV.
- Incident infections, including SARS-CoV-2, STIs, CMV, toxoplasmosis, and EBV, and the resulting immune activation, will lead to HIV disease progression and potentiate end-organ disease.
- Vaccine hesitancy will be less common among YAPHIV than YAPHEU.
- YAPHIV when compared to YAPHEU will be at increased risk of periodontal disease, resulting in local and systemic immune activation and alterations in the oral microbiome, which in turn will hasten the decline in oral health.
- Bone loss in YAPHIV will be associated with ARVs and immune activation.
- Both knowledge and use of PrEP by YAPHEU will be low; HIV infection will be uncommon.
- Use of PrEP will increase over time, but use of PrEP and its rate of change over time will vary by sex.

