2.2.4 Sexually Transmitted Infections

Specific Aims:

- To evaluate access to testing and treatment for genital STIs and bacterial vaginosis, and the incidence of and risk factors for acquiring STIs (e.g., *C. trachomatis*, *N. gonorrhoeae*, *T. vaginalis*, syphilis, HPV, HSV) and microbiome dysbiosis including clinical bacterial vaginosis among YAPHIV and YAPHEU, and acquisition of HIV among YAPHEU.
- To evaluate the incidence of and risk factors for pelvic inflammatory disease among females.

- To evaluate the occurrence of HSIL, external genital warts, and persistent cervical, oral, and anal high-risk HPV, and the factors associated with persistent anogenital or oral high-risk HPV, including the vaginal microbiome.

Hypotheses:

- YAPHIV will have similar frequencies and risks as YAPHEU for acquiring STI infections such as *C. trachomatis*, *N. gonorrhoeae*, and *T. vaginalis*. On the other hand, infections such as HPV, bacterial vaginosis and HSV will be found more frequently in YAPHIV and will be associated with lower CD4 cell counts.
- The risk of pelvic inflammatory disease will be higher in female YAPHIV since there is evidence that the vaginal dysbiosis that has been linked to pelvic inflammatory disease will be more common in female YAPHIV.
- Genital high-risk HPV persistence and its associated risk of HSIL will be higher in WLPHIV than for women without HIV and WLPHEU. Risk factors for high-risk types of HPV persistence and development of HSIL will include vaginal dysbiosis and its associated inflammatory states, low CD4 cell counts, smoking, and substance use. Similar risk factors will be associated with external genital warts. Women who received HPV vaccination before the onset of sexual debut will be at lower risk of HSIL and external genital warts.

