4.2 YAPHEU Cohort

4.2.1 Inclusion Criteria

To be considered eligible for enrollment, an individual must meet all the criteria listed below:

- Is living with perinatal HIV exposure and without perinatally acquired HIV.

- Is at or beyond their 18th birthday at the time of informed consent.
- Is willing to provide access to existing medical records.
- Is willing to participate and provide legal written consent.

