4.2.2 Exclusion Criteria

To be considered eligible for enrollment, an individual must not:

- Have confirmed perinatal HIV infection as documented in the medical record.

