Annual Web-Based Survey ³	The following categories of questions will be included in the annual surveys: socio-demographics, general health and health care-related, mental health, social determinants of health, reproductive health, sexual behaviors, and substance use.											To be completed on any device with access to the internet, including a cell phone. Most questions are part of a single primary survey, but some may be administered separately as a short, stand-alone survey.
Additional Web-based Surveys	In addition to the evaluations specified in the protocol, completion of occasional brief voluntary web-based or interview-administered surveys by participants may be requested to address specific time-sensitive or important issues as they arise. The content of these additional surveys will fall under the aims of the protocol and be covered by the informed consent, with notification of the HLC IRB as required.											
Chart Abstraction⁴												
Interval diagnoses, medications ⁵ , and family history	X	X	X	X	X	X	X	X	X	X	X	
Results of lab tests conducted for clinical care ⁶	X	X	X	X	X	X	X	X	X	X	X	
Height, weight, and blood pressure	X	X	X	X	X	X	X	X	X	X	X	

	Entry (Year 0) ¹	Year										Comments
		1	2	3 ¹	4	5	6 ¹	7	8	In-person visits (9, 12...) ¹	Years without in- person visits (10, 11, 13, 14...)	
Laboratory: Real-Time Testing												
STI testing ⁷	X	X	X	X	X	X	X	X	X	X	X	--Self-collect in clinic at Entry and the in-person follow-up visits (e.g., Years 3, 6, 9, 12...) --Self-collect at home and deliver/mail to clinic at all other years --Do not perform if results are available for both N. gonorrhoeae and C. trachomatis within the past 12 months --Males: urine --Females: vaginal swab #1 or urine if swab is declined
HIV test ⁸				X					X			Also abstract results for any test conducted after the Entry visit
Laboratory: Central Testing⁹												
Urine for renal biomarkers	X			X			X			X		Collect in clinic
Serum for cardiac biomarkers	X			X			X			X		Collect in clinic
Fasting serum lipids	X			X			X			X		Collect in clinic
Fasting plasma glucose and serum insulin	X			X			X			X		Collect in clinic
Research Aptima STI testing ¹⁰	X	X	X	X	X	X	X	X	X	X	X	--Self-collect in clinic at Entry and the in-person follow-up visits (e.g., Years 3, 6, 9, 12...) --Self-collect at home and deliver/mail to clinic at all other years --Males: urine Females: vaginal swab #2 or urine if swab declined
Repository												

	Entry (Year 0) ¹	Year										Comments

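### The Year 0–3 HIV acquisition rate in YAPHEU is open to upward bias from infection already present at Entry, because the plan schedules no HIV test at Entry and its HIV row collects none from before it

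*Protocol*

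**What the plan says.** **Aims.** Section 2.2.1: "Among YAPHEU, to determine their level of knowledge about and use of PrEP and their rates of HIV acquisition". Section 2.2.4 places "and acquisition of HIV among YAPHEU" inside the aim on STI incidence and risk factors. The related hypothesis in 2.2.1 is "Both knowledge and use of PrEP by YAPHEU will be low; HIV infection will be uncommon"; no expected rate is given.

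**Eligibility.** Section 4.2.1 requires that a participant "Is living with perinatal HIV exposure and without perinatally acquired HIV". Section 4.2.2 says a participant must not "Have confirmed perinatal HIV infection as documented in the medical record". Neither asks for a negative HIV test, and neither addresses HIV acquired by another route before enrolment.

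**Scheduled tests.** Section 6.4: "YAPHEU will have an HIV test performed in real-time at a local clinical lab at the Years 3 and 9 in-person study visits". The study abstract and Section 9.9 describe the same test as offered.

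**Chart data.** The HIV row of Appendix II adds: "Also abstract results for any test conducted after the Entry visit". Notes 4 and 5 of Appendix II limit the Entry abstraction to the preceding 12 months and ask for all medical diagnoses to be recorded.

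**Stored blood.** Serum and plasma go to the repository at Entry and every third year (Appendix II). Their use is left open (Section 6.6), and participants may decline storage (Section 13.6.1).

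**The concern.** A rate of acquisition needs a group known to be uninfected at the start and a date, or at least an interval, for each infection. For Years 0 to 3 the plan supplies neither. Participants are adults at enrolment, and Section 1.1.9 reports that more than half of AMP youth aged 16 to 18 had already had vaginal or anal sex, so exposure before Entry is real.

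The Protocol sets a starting condition for other outcomes. Section 12.2.4 counts incident LSIL and HSIL only in women whose first Pap smear was normal. Section 12.2.2 builds metabolic incidence on participants free of the risk factor at baseline. HIV acquisition has no counterpart.

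What is at stake is a rate built on very few events, in which one misclassified infection could be a large share of the numerator. An analysis plan cannot repair this later if the pre-Entry test was never abstracted.

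**Working it through.** **Inputs.** Scheduled tests at Years 3 and 9 (Section 6.4); about 200 YAPHEU (Section 3.2); 6% yearly loss in YAPHEU (Section 12.1.1). The Protocol gives no acquisition rate to reproduce. The loss figure can be checked: 200 × 0.94^11 = 101.3, which matches the 101 in Section 12.1.1. Assumed, because the document gives none of them: y, the sexually active years before Entry; p, the prevalence of undiagnosed HIV at Entry; λ, the yearly infection rate.

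**1. Upper bound with equal rates before and after Entry.** For a rare infection and no testing before Entry, expected positives at Year 3 are proportional to λ(3+y), while true on-study acquisitions are proportional to 3λ. The ratio is (3+y)/3:

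| y (years, assumed) | Years 0–3: (3+y)/3 | Both tests pooled, no attrition: (9+y)/9 |
|---|---|---|
| 1 | 1.33 | 1.11 |
| 3 | 2.00 | 1.33 |
| 5 | 2.67 | 1.56 |

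**2. In numbers of infections.** Participants left at Year 3: 200 × 0.94^3 = 166.1. Pre-Entry infections found then: 166.1 × p. On-study infections: 166.1 × (1−p) × (1−exp(−3λ)). Three of the nine combinations examined (the two extremes and the middle):

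| p | λ per 100 person-years | Pre-Entry | Acquired on study | Pre-Entry share | Apparent/true rate, Years 0–3 |
|---|---|---|---|---|---|
| 0.25% | 0.5 | 0.42 | 2.47 | 14% | 1.17 |
| 0.5% | 0.25 | 0.83 | 1.24 | 40% | 1.67 |
| 1% | 0.1 | 1.66 | 0.49 | 77% | 4.37 |

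Ratios use unrounded counts. The two calculations agree, because p/λ acts as y: 0.5, 2 and 10 years give (3+y)/3 = 1.17, 1.67 and 4.33. The last row exceeds the 2.67 of step 1 because it implies ten years of exposure at the on-study rate, or a higher rate before Entry than after. The bound in step 1 therefore depends on its equal-rate assumption.

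**3. Years 3 to 9.** Anyone negative at Year 3 has a documented baseline. With 6% yearly loss, person-time under observation is 200 × (0.94^3 − 0.94^9)/(−ln 0.94) ≈ 830 person-years, and 200 × 0.94^9 = 114.6 participants remain for the Year 9 test. Refusals at Year 3 would lower both figures.

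**4. Dating.** Without clinical tests in between, an infection is located only within 3 years (Entry to Year 3) or 6 years (Years 3 to 9). These gaps can lengthen: a missed in-person assessment may move to the next annual visit (Section 8.1), and participants followed through the data centre have no laboratory assessments (Section 8.3).

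**The case against.** The strongest reply is that the plan has more sources of HIV status than the two scheduled tests. Clinical HIV tests after Entry are abstracted, so an early negative can supply a baseline and later results narrow the interval. A diagnosis charted in the 12 months before Entry would be recorded. This stands. It confines the bias to infections undiagnosed at Entry or diagnosed before the look-back, and makes the 3- and 6-year intervals the case where clinical care adds nothing.

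It is also fair that (3+y)/3 is a worst case for Years 0–3 only, that infection is expected to be uncommon, and that test frequency in an observational cohort is a trade-off against burden. Interval censoring and counting rules could sit in an analysis plan that is not shown. Eligibility, abstraction fields and use of specimens are protocol matters.

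A reader might infer three stronger things that the document does not support:

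- That the acquisition aim cannot be met. The Year 3–9 rate among Year 3 negatives is estimable, and stored Entry plasma can settle earlier cases where storage was agreed.
- That the Protocol counts infections from before enrolment as acquired on study. No section says so; the risk follows from having no baseline and no classification rule.
- That undetected infections materially contaminate the uninfected comparison group. On the assumptions above, about 0.4 to 1.7 infections present at Entry would be found among 166 participants at Year 3. No effect on the neurocognitive, metabolic or STI contrasts has been shown.

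**Conclusion.** The point holds for the Year 0–3 rate. Followed as written, the plan cannot separate a non-perinatal infection present but unrecognised at Entry, or diagnosed before the look-back, from one acquired by Year 3. The error runs upward. Its size is at most 1.33-, 2.0- or 2.67-fold for 1, 3 or 5 assumed years of exposure before Entry, provided nobody was tested before Entry and the rate was the same before and after it. Across the assumed prevalence and incidence ranges it runs from about 1.2- to 4.4-fold, on one or two misplaced cases at most. Earlier testing, or clinical tests soon after Entry, would shrink it. The Year 3–9 rate among Year 3 negatives does not carry this bias, though its infection dates may be uncertain by up to 6 years. The weakness concerns one outcome within two aims and is cheap to correct.

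**What to change.** 1. In the HIV row of Appendix II, also abstract the result and date of the most recent HIV test before Entry, and flag any known non-perinatal HIV at Entry.
2. For a participant first found positive at Year 3, test the stored Entry plasma; for one first found positive at Year 9, test the Year 6 plasma. Do this only where storage consent exists. Count an infection as acquired on study only if there is a documented negative at Entry or later, or within a stated short window before Entry. Treat its date as interval-censored between last negative and first positive.
3. Reconcile Section 6.4, which has the test performed, with the abstract and Section 9.9, which have it offered. Refusals change the denominator.

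Extending the exclusion in Section 4.2.2 to documented HIV by any route is not needed. It would not reach undiagnosed infection, and the flag in item 1 handles known cases.

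**Cost.** One abstraction field, assays on a handful of stored specimens and a few lines of text. The drawback is that participants with no documented negative contribute no person-time to the acquisition rate until their first negative test, so the Year 0–3 estimate will rest on fewer people.
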